7.8.2 Laboratory data

The analyses of laboratory data will be descriptive in nature and will be based on BI standards “Display and Analysis of Laboratory Data” ([7](#)). CTC grade for applicable lab parameters will be calculated according to CTCAE v5.0 ([6](#)).

Descriptive statistics of all converted laboratory values by visit will be provided including changes from baseline. Frequency tables of transitions relative to the reference range and of possible clinically significant abnormalities will be produced. For those parameters that have CTC grading possible clinically significant abnormalities are defined as those laboratory values with a CTC grade ≥ 2 that have had an increase of ≥ 1 grade from baseline. For those parameters for which no CTC grade has been defined standard BI project definitions will be used to decide on clinical significance. Further frequency table will show the transition of CTC grade from baseline to worst value and from baseline to last value on treatment.

Summaries will be produced of laboratory data recorded at screening, on-treatment and post-study periods. For details on the treatment definition, see [Section 6.1](#).

Differential blood counts will be displayed in absolute value. In case a subject's differential blood count is reported in percentage, the following conversion will be applied:

Differential blood count [10⁹/L]:

Differential [10⁹/L] = Differential [%] *white blood cell count / 100

The corresponding reference ranges of the converted differential blood values are not allowed to be converted like the individual laboratory measurements. The reference range is taken from BI standard reference range definition.

The focus of the laboratory data analysis will be on the following laboratory parameters:

- Low values: Activated Partial Thromboplastin Time (aPTT), Prothrombin Time (PT), International Normalised Ratio (INR), White Blood Cell Count (WBC) with differential, Platelets (PLT)
- High values: Aspartate Aminotransferase (AST), Alanine Aminotransferase (ALT), bilirubin, Alkaline Phosphatase (AP), Activated Partial Thromboplastin Time (aPTT), Prothrombin Time (PT), International Normalised Ratio (INR), Protein levels in urine

7.8.3 Vital signs

Descriptive statistics of all vital signs measurement by visits are planned for each dose levels.

The frequency of patients with increased blood pressure by highest CTC grade (grades 1, 2, 3 and all grades) and prior history of hypertension will be summarized. For the patients with hypertensive blood pressure measurements, frequency will be summarized by time to onset of hypertensive episode after infusion for each dose levels. Their duration and outcome of first hypertensive episode will also be reported. Any hypertension defined as grade 2 or higher will be shown with detailed increase date and administration information.

7.8.4 ECG

[figure not shown]
ECG data will be collected as described in CTP section 5.2.5. Clinically significant findings in ECG data will be reported under "Adverse events" if applicable and will be analysed accordingly.

[figure not shown]

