5.2.5 Electrocardiogram

The 12-lead ECGs must be performed at the time points specified in the Flow Chart. The investigator or a designee will evaluate whether the ECG is normal or abnormal and assess clinical relevance. ECGs may be repeated for quality reasons and a repeated recording used for analysis.

On the days of administration, ECG should be taken at two time points:

1. pre-dose (-60 min. to -5 min.)
2. shortly before the end of the infusion of trial medication.

In case of drug-related ECG changes and whenever the investigator deems necessary, additional ECG monitoring will be performed in the respective and later cycles of treatment. Cardiac monitoring for patients presenting a QTc interval prolongation CTCAE grade ≥ 3 shall be followed as follows:

- Continuous ECG monitoring until the QTc interval < 470 ms
- Cardiologist opinion for potential treatment of this event as soon as the QTc interval prolongation is observed.
- Cardiologist recommendation after QTc interval normalisation (< 470 ms) and potential follow-up.

In order not to confuse ECG recording, PK samples should be taken after performing the ECG. Decision on patient's eligibility will be taken based on Investigator medical opinion. Pathological ECG results will be recorded as AEs by the investigator.

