5.7 APPROPRIATENESS OF MEASUREMENTS

All measurements performed during this trial are standard measurements and will be performed in order to monitor subjects' safety and to determine pharmacokinetic and pharmacodynamic parameters in an appropriate way. The scheduled measurements will allow monitoring of changes in vital signs, standard laboratory values, and ECG parameters that might occur as a result of administration of trial medication. The safety assessments are standard, are accepted for evaluation of safety and tolerability of an intravenously administered drug, and are widely used in clinical trials. The pharmacokinetic parameters and measurements outlined in Sections [2.1.3](#), [2.2](#), and [5.3](#) are generally used assessments of drug exposure. The biomarkers and pharmacodynamic parameters and measurements outlined in Section [5.4](#) are of exploratory nature only. The determination of the immunogenic response before or during treatment with NBEs is generally applied to monitor immunogenicity risks.

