7.3.5 Safety analyses

Adverse events will be coded using the Medical Dictionary for Drug Regulatory Activities (MedDRA). Standard BI summary tables and listings will be produced. All adverse events with an onset between start of treatment and end of the REP, a period of 42 days after the last dose of trial medication, will be assigned to the on-treatment period for evaluation.

All treated patients will be included in the safety analysis. In general, safety analyses will be descriptive in nature and will be based on BI standards. No hypothesis testing is planned.

Statistical analysis and reporting of adverse events will concentrate on treatment-emergent adverse events, i.e. all adverse events occurring between start of treatment and end of the REP. Adverse events that start before first drug intake and deteriorate under treatment will also be considered as ‘treatment-emergent’.

Frequency, severity, and causal relationship of adverse events will be tabulated by system organ class and preferred term after coding according to the current version of the MedDRA at database lock.

Laboratory data will be analysed both quantitatively as well as qualitatively. The latter will be done via comparison of laboratory data to their reference ranges. Values outside the reference range as well as values defined as clinically relevant will be summarised. Treatment groups will be compared descriptively with regard to distribution parameters as well as with regard to frequency and percentage of patients with abnormal values or clinically relevant abnormal values.

Vital signs, physical examinations, or other safety-relevant data observed at screening, baseline, during the course of the trial and at the end-of-trial evaluation will be assessed with regard to possible changes compared to findings before start of treatment.

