4. CHANGES IN THE PLANNED ANALYSIS OF THE STUDY

This section is not applicable.

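### SAP 7.8.4 reports ECG data only through investigator-judged adverse events, so the repeated QTcF readings enter no numeric summary and a moderate shift could go unnoticed

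*SAP*

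**What the plan says.** SAP 7.8.4 has two sentences. The first defers to the protocol: "ECG data will be collected as described in CTP section 5.2.5". The second says that "Clinically significant findings in ECG data will be reported under" adverse events and will be analysed as such. It plans no by-visit statistics, change from baseline or threshold count for any ECG parameter.

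Protocol 5.2.5 sets out the route from recording to AE. "The investigator or a designee will evaluate whether the ECG is normal or abnormal and assess clinical relevance", and "Pathological ECG results will be recorded as AEs by the investigator". It asks for two recordings on each dosing day, one before dosing and one "shortly before the end of the infusion of trial medication". The Flow Chart adds screening, Day 2 of cycles 1 and 2, and the end-of-treatment visit. QTcF above 470 ms at screening excludes a patient (Protocol 3.3.3, criterion 9), and QTcF must be at or below 470 ms before each further cycle (Protocol 4.1.6).

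On analysis, Protocol 7.3.5 says that vital signs, physical examinations or other safety-relevant data "will be assessed with regard to possible changes compared to findings before start of treatment". Protocol 5.7 adds: "The scheduled measurements will allow monitoring of changes in vital signs, standard laboratory values, and ECG parameters". SAP Section 4, on changes to the planned analysis, reads "This section is not applicable".

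**The concern.** QTcF is a continuous quantity read many times per patient, including near the end of infusion, when concentrations are close to their highest. The plan keeps only what an investigator judges clinically significant. A modest change present in most patients can leave every one of them below that judgement, and then nothing appears in the report.

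ECG also stands out within the SAP. Laboratory values get by-visit statistics with change from baseline (7.8.2), vital signs get by-visit statistics per dose level (7.8.3), LVEF gets percent change (7.8.5) and ECOG status gets best, worst and last (7.8.6). No reason is given for treating ECG differently. At stake is the completeness of the safety description in a small phase I trial.

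**Working it through.** The documents give no QTcF mean, variance or planned ECG figure, so there is nothing of the plan's own to reproduce. The check has three parts: a count from the schedule, an illustration of how a shift can stay hidden, and the precision that a summary would have.

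**1. Scheduled ECGs per patient (Flow Chart and Protocol 5.2.5).** For c cycles: screening 1 + 2c on dosing days + Day 2 in cycles 1 and 2 + end of treatment 1.

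- c = 2: 1 + 4 + 2 + 1 = 8
- c = 4: 1 + 8 + 2 + 1 = 12
- c = 6: 1 + 12 + 2 + 1 = 16

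None of these readings enters a numeric summary.

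**2. How many patients would cross 470 ms?** This is the protocol's own QTcF limit, used here as a stand-in for a clinical threshold. Assumptions: between-patient SD 20 ms; baseline mean m of 400, 415 or 430 ms; a uniform shift s; one reading per patient; about 24 patients in the trial (Protocol 7.6: about 9 plus about 15). Expected number above 470 ms = 24 × [1 − Φ((470 − m − s)/20)].

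| Assumed baseline mean | s = 0 | s = 10 ms | s = 20 ms |
|---|---|---|---|
| 400 ms | 0.01 | 0.03 | 0.15 |
| 415 ms | 0.07 | 0.29 | 0.96 |
| 430 ms | 0.55 | 1.60 | 3.81 |

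For example, m = 415 and s = 10 give z = 45/20 = 2.25, a tail probability of 0.0122, and 24 × 0.0122 = 0.29. At the lower and middle baselines, a 10 ms shift in every patient puts fewer than one expected patient over the limit. Repeated readings would raise the chance of a crossing, so the table indicates scale only.

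**3. Precision of a mean change from baseline.** 95% CI half-width = t(0.975, n − 1) × SD/√n, for an assumed SD of within-patient change of 10 to 20 ms.

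| n | Where it arises | Half-width, SD 10 | Half-width, SD 20 |
|---|---|---|---|
| 3 | minimum cohort (Protocol 3.1) | 4.303 × 10/√3 = 24.8 ms | 49.7 ms |
| 6 | patients at the MTD (Protocol 7.1.1) | 2.571 × 10/√6 = 10.5 ms | 21.0 ms |
| 9 | Part I, all doses | 2.306 × 10/√9 = 7.7 ms | 15.4 ms |
| 15 | Part II, all doses | 2.145 × 10/√15 = 5.5 ms | 11.1 ms |

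A dose-level row alone could not resolve a shift of about 10 ms. Pooling within a part brings the interval into a range where such a shift could be described, most clearly in Part II.

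**The case against.** The strongest reply is that the SAP does what the protocol says about ECGs. Protocol 5.2.5 sends pathological results to AE reporting, and Protocol 5.2.9.1.1 does the same for ECG changes judged clinically relevant. Protocol 7.3.5 does not name ECG and promises no particular statistic, and Protocol 5.7 speaks of monitoring, not of analysis. A reader might infer that the SAP breaks a protocol commitment and that Section 4 conceals it. The documents do not support that: the SAP is narrower than 7.3.5 and 5.7 read together, and no more than that can be said.

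A reader might also infer that a systematic QTcF effect could not be seen at all, or that ECG is reduced to a yes/no outcome. Neither holds. SAP 7.8.1 tabulates AEs by highest CTC grade, relatedness and seriousness, with separate tables for events leading to dose reduction or discontinuation. A non-haematological toxicity of Grade 3 or above is a potential DLT (Protocol 4.1.7), and QTcF above 470 ms delays the next cycle (Protocol 4.1.6). Larger shifts would leave a trace.

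It is also tempting to argue from power, setting a paired test in 24 patients against a test on the count above 470 ms. That comparison should not be made. No hypothesis testing is planned (Protocol 7.2), nobody plans a test on that count, every input would be assumed, and 24 patients pools monotherapy with combination therapy.

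Two further points stand. No QT concern is stated: monkey studies showed no ECG effect for either drug (Protocol 1.2.1 and 1.2.2), and the risk table in Protocol 1.4.2 lists none. And Protocol 5.2.3 says that blood pressure values go into the eCRF, whereas 5.2.5 says nothing of the kind for QTcF. These points lower the priority. They do not explain why values that must be read for eligibility and retreatment should go unsummarised.

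**Conclusion.** The point holds as a low-cost improvement to the SAP, not as an error. As visible, SAP 7.8.4 contains no numeric ECG analysis, and a moderate QTcF shift below the level of clinical judgement could pass unreported. Parts of the SAP are redacted and SAP 7.8.1 mentions a technical TSAP, but 7.8.4 refers to no other ECG output.

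The gain is modest and descriptive. It lies mainly in the rows pooled within each part, because dose-level cohorts of 3 to 6 are too small for a useful interval. These sizes rest on the assumed SD of change and on the expected patient numbers of about 9 and 15. MTD determination does not depend on any of this.

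**What to change.** In SAP 7.8.4, keep the AE reporting and add:

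- Descriptive statistics of QTcF and its change from baseline at each scheduled time point, with end of infusion shown separately, per dose level and pooled within Part I and within Part II.
- A 95% CI for the pooled mean change in each part.
- The maximum post-baseline change per patient, and the number of patients with any post-baseline QTcF above the protocol's 470 ms limit.

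Baseline should be the one in SAP 6.6, the last value before first administration, and not each cycle's own pre-dose value. With half-lives of 197 to 343 hours (Protocol 1.2.1), a cycle-specific baseline could remove part of a persistent shift. Because SAP 6.6 allows same-day values and refers to clock time only for laboratory data, the text should say that the first-dose end-of-infusion ECG cannot serve as baseline.

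The cost is one or two tables and a few lines of text. The condition is that numeric QTcF is in the trial database; if it is held only at sites, it must be transferred. If it cannot be obtained, SAP Section 4 should state that ECG data are analysed through AEs only, and why.

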7.8.5 Echocardiography

Descriptive statistics are planned for this section. A table shows LVEF at screening, EOT visit and percent change from baseline to final will be provided.

7.8.6 ECOG performance status

[figure not shown]
The best, worst and last ECOG performance status during treatment will be summarized by treatment and baseline status for Part I and Part II separately.

[figure not shown]

